This study is designed to compare the relative effectiveness of two transvaginal apical suspension strategies for uterovaginal prolapse: a mesh augmented hysteropexy vs. vaginal hysterectomy and uterosacral ligament suspension. Power and sample size calculations were generated to determine the sample size needed to test for treatment difference favoring the mesh augmented strategy (i.e., a superiority trial) across the study arms for a variety of assumptions about effect size and study follow-up time. For all power analyses, we assumed that failure in both arms follows an exponential survival model and that the native tissue repair has a success rate of 80% at 24 months. This 80% calculation is based on an assumed 85% anatomic success rate for uterosacral ligament suspension (Table 2) and an additional 5% failure rate based on symptom failure. In the only published Uphold® series there is a 98% 12 month anatomic success rate.³² Although no 2-year outcome data are available for the Uphold® procedure, under an assumption of a constant hazard, the 1-year success rate of 98% yields an estimated 2-year anatomic success rate of 96%; combining this estimate with a similar 5% rate for symptom failure yields a 91% composite (anatomic and symptom) success rate. All analyses also assumed that statistical tests would be conducted with a Type I error rate of 0.05 with adjustment for multiple comparisons based on a single interim analysis. Sample size estimates assumed that the 2-year success rate in the mesh-augmented arm is in the range of 90% to 93% at 24 months (note that this represents a hazard ratio in the range of 0.33 to 0.47 under the assumed exponential survival model), that the enrollment time for the study is 2 years, the loss-to-follow-up on both arms is no more than 5% per year, and the total study duration from last participant enrolled to primary outcome analysis is 36 months with one interim analyses for efficacy when the last participant reaches the 24-month follow-up. Table 7 provides estimates of the power for the different assumptions for total sample sizes in the range of 160 to 300 participants under the assumption that a single interim analysis will be conducted using O’Brien-Fleming stopping rules.

Table 7. Sample Size Calculations

Total Sample Size	Power as a Function of 2-Year Effect Size—with Base 2-Year Success of 80% and 36-Month Follow-Up After Last Enrollment and a 2-Year Enrollment Period			
	$\Delta=0.10$ HR=0.472	$\Delta=0.11$ HR=0.423	$\Delta=0.12$ HR=0.374	$\Delta=0.13$ HR=0.325
160	0.87	0.93	0.96	0.99
180	0.89	0.95	0.98	0.99
200	0.92	0.96	0.99	>0.99
220	0.94	0.98	0.99	>0.99
240	0.96	0.98	0.99	>0.99
260	0.95	0.99	0.99	>0.99
280	0.98	0.99	>0.99	>0.99
300	0.98	0.99	>0.99	>0.99

Based on these calculations, a total of 180 participants will be randomized at a 1:1 ratio to the two treatment arms. This sample size will provide a power of 0.89 to detect an additive difference of 10% in the 2-year success rate (i.e. a hazard ration of 0.472) and a power of 0.95

Confidential Please Do Not Copy

to detect additive differences of 11% or greater in the 2-year success rate (hazard ratios of 0.423 or less).

One of the advantages of the survival analysis approach is that the study continues to accumulate information on individuals enrolled early in the study as they have events beyond a fixed two-year or three-year time frame, particularly for a study like this one in which successes are more likely to occur than are failures over the first three years. As such, the survival approach with multiple looks will allow the analysis of the primary outcome of overall risk of treatment failure for the study to be completed and results published, while still collecting information on longer-term outcomes.

O. Statistical Design

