4. Performance of or has received hands-on proctoring on at least 5 Uphold® procedures for uterovaginal prolapse or cuff-vaginal prolapse. Surgeons who meet all the criteria except the Uphold® procedure experience criteria may enroll participants in the SUPeR study; however, if the participant randomizes to the Uphold arm, the surgery will be proctored by a certified study surgeon. This certified surgeon will be scrubbed in and provide hands on supervision for the anterior dissection, Capio placement of the mesh arms, tensioning parts of the procedure, and incision closure. The certified proctoring surgeon will be the study surgeon of record and takes full responsibility for the performance and the quality of the procedure. The procedure may be counted as a proctored procedure for the other surgeon.
5. Prior to signing off on certification for each site's surgeon, the site PI will review these 5 cases for any Uphold® procedure related complications and may request additional proctoring or experience before approving certification of that surgeon.

Surgical Education and Monitoring

At baseline, all study surgeons will provide data on their training, surgical volume, and length of time in practice. On a quarterly basis, all study surgeons will provide the number of uterovaginal apical suspensions that they performed outside of the SUPeR study. The surgical videotapes or DVD's illustrating essential components of the uterosacral vault suspension technique and Uphold® technique will be made available and distributed to each participating surgeon, along with a detailed written description of the technique and guidelines for concurrent procedures. The videotape/DVD and written material will be reviewed and discussed at an in-person PFDN Steering Committee meeting at a time shortly before enrollment begins. Each Principal Investigator at the clinical sites will be responsible for reviewing and discussing the videotape and written materials with participating surgeons at his/her site (before enrollment begins).

Certified Surgeons as Teachers

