All sites in the Pelvic Floor Disorders Network are teaching institutions and have accredited fellowship programs in Female Pelvic Medicine and Reconstructive Surgery. Residents and fellows may assist at surgery for SUPeR participants. The certified surgeon is always the surgeon of record for the study and takes full responsibility for the performance and the quality of the procedure. The certified surgeon will be scrubbed in and will perform (or provide hands-on supervision) of the procedure. The certified surgeon assumes full responsibility for assuring proper uterosacral ligament suture placement, attachment of these sutures to the vagina, anterior dissection for the Uphold® procedure, Capio placement of the mesh arms, tensioning parts of either procedure, and incision closure.

Confidential Please Do Not Copy

J.2 Description of Surgical Procedures

Uterosacral Ligament Suspension (ULS)

The ULS procedure used in this protocol is a modification of the technique described by Shull.¹³

1. ULS is performed through a vaginal incision.
2. The placement of uterosacral ligament stitches will be performed in such a way as to avoid neurovascular and ureteral compromise.
3. One permanent and one delayed absorbable 0 or 2-0 monofilament suture (2 sutures per side; 4 sutures total) must be placed in each ligament, extending to the ipsilateral anterior and posterior fibromuscular wall of the vaginal apex. The permanent sutures will be placed near full thickness, excluding vaginal epithelium. The delayed absorbable sutures will be placed full thickness through the vaginal wall with the knot tied inside the vaginal canal. The type of suture material will be recorded.
4. The use of a pulley stitch is allowed.
5. No plication of the uterosacral ligaments across the midline or culdoplasty is allowed.
6. Other aspects of the suspension procedure will be left to surgeon preference but will be recorded.
7. In the event that clinical circumstances prohibit safe/effective completion of the planned procedure, the preferred back-up procedure is a SSLF. In the unlikely event that both ULS and SSLF cannot be performed safely or effectively, the choice of vaginal suspension procedure will be left to the surgeon's discretion and recorded.

Uphold® Procedure

The Uphold® procedure used in this protocol is a modification of the technique described by Vu and Goldberg.³²

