1. Hydrodissection of the vaginal walls will be performed with at least 30 cc of 0.25% bupivacaine with epinephrine or dilute Pitressin (20 Units/50-100 cc).
2. An approximate 4 cm transverse vaginal incision is made in the anterior vagina wall between the bladder neck and the cervix but at least 3 cm from the cervix so that the suture line will not overlap with the mesh.
3. Blunt or sharp dissection to approach the sacrospinous ligament extraperitoneally.
4. After confirmation of the location of the ischial spine, the tapered lead and mesh assembly will be delivered into the SSL 1-2 fingerbreadths medial to the ischial spine.
5. The most cephalic edge of the mesh will be attached to the cervix with sutures.

6. Mesh modifications (e.g. cutting) are strongly discouraged; any exceptions will be documented on operative case report forms.
7. Tensioning to re-suspend the apex without tense mesh arms.
8. Vaginal closure with 2-0 polyglactin.
9. Placement of a vaginal pack and Foley catheter removed on POD1.

For all procedures:

1. The study surgeon is responsible for meeting the experience requirements, is the surgeon of record, and will be present and scrubbed in for key portions of the procedure. Residents or fellows may participate in procedures as is standard for each Clinical Site.
2. Cystoscopy with intravenous indigo carmine dye (or an appropriate substitute) performed at the end of the procedure after all vault suspension sutures are tied or after the Uphold® straps are adjusted and is required as a standard part of the surgical procedure.
3. Prophylaxis against deep vein thrombosis is required for all participants. The method may be chosen by each surgeon.
4. Preoperative intravenous antibiotic prophylaxis is required as part of the surgical procedure. The details (choice of antibiotic, dose, etc.) will be determined by each surgeon.
5. All concomitant native tissue procedures must be declared and recorded prior to randomization. The surgeon has the discretion to alter from this preoperative plan as necessary to achieve the desired anatomic result. Any such alterations must be recorded.

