 - b) Urinary – urinary function including duration of post-op catheterization, mean UDI-6 scores⁴⁹, Hunskar Incontinence Severity Index, de novo voiding dysfunction rates, de novo incontinence rates
 - (i) Sexual – mean PISQ-IR⁵⁰ and specific rates of de novo dyspareunia
 - (ii) Bowel – bowel function using CRADI-8 scores⁴⁹
 - (iii) QOL – general SF-12 scores and sub-scales⁵¹, and Pelvic QOL mean PFIQ score⁴⁹; Functional Activity Assessment Scale⁴²

Secondary Aim 2 – Safety: These measures will require a statistical analysis plan and will be reported in the primary outcome manuscript.

- 1) Intraoperative safety – group comparisons of mean Operative time, estimated blood loss, blood transfusion, intra- and post-operative complications categorized using a modification of the Dindo Classification.⁵²
- 2) Adverse events – mesh related complications: mesh exposure in the vagina or mesh erosion into another organ and the classification of the intervention:
 - a) none or non-surgical medical intervention only

Confidential Please Do Not Copy

- b) minor or intra-office surgical intervention
- c) outpatient surgery
- d) inpatient surgery

Other complications possible in both arms:

- 1) Rates of pain captured from the modified Surgical Pain Scale⁴³, pain medication use, and location of pain with Pain Mapping Instrument
- 2) Pelvic infection:
 - a) perioperative infections
 - b) urinary tract infections
 - c) vaginal infections with flora uncommon to the vaginal canal
- 3) Vaginal shortening, de novo vaginal bleeding, atypical vaginal discharge, fistula formation, neuromuscular problems (including groin and leg pain)
- 4) Need for subsequent procedures – any surgical or non-surgical treatment for pelvic floor disorders (including urinary incontinence, voiding dysfunction, defecatory dysfunction or fecal incontinence, recurrent prolapse, and dyspareunia/pelvic pain). Any subsequent uterine or cervical office or Operating Room procedure in hysteropexy group (e.g., cervical biopsy, LEEP, hysteroscopy, D and C, hysterectomy).
- 5) Subsequent uterine or cervical pathology
- 6) Rates of vaginal scarring defined as de novo vaginal scar requiring medical or surgical intervention or adversely affecting quality of life
- 7) Rates of vaginal shortening, de novo dyspareunia, and worsening dyspareunia with AE survey instrument

Complication Monitoring

Groups will be compared for rates of “important complications”. The definition of “important complication” is:

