3.2 Outcomes

The **primary outcome** for the study is treatment failure at any point after the participant leaves the operating room; note that per protocol requirements, the patient cannot leave the operating room

as a treatment failure. A participant will be considered a treatment failure if any ONE of the following criteria is met:

- 1) Report of bothersome vaginal bulge symptoms (see definition below), or
- 2) Re-treatment for prolapse (surgery or pessary), or
- 3) Any prolapse measure (Ba, C, Bp) is beyond the hymen (i.e. >0 cm)

Bothersome vaginal bulge symptoms = positive response to Question 3 of the PFDI-20: Do you usually have a bulge or something falling out that you can see or feel in your vaginal area? AND any degree of bother. This single question has been identified to most accurately and reliably identify those women with POP. An affirmative answer to this question was 96% sensitive (95%CI 92-100) and 79% specific (95%CI 77-92) for prolapse beyond the hymen. The 1-week test-retest reliability was good (kappa .84).

Participants not considered a treatment failure for the primary outcome will be considered a treatment success.

A number of secondary outcome measures will be used to support the analyses for the secondary aims listed earlier. Outcomes that will be used in the planned analyses associated with each of the secondary aims include:

- 1. Anatomical measures of treatment efficacy in the two treatment arms obtained at 6-month intervals after surgery:
 - a. Mean and median POPQ point (Ba, Bp, C) location measures postoperatively in the two treatment arms.
 - b. Proportion of participants in each group with C > -1/2 TVL
- 2. Functional measures of treatment efficacy in the two treatment arms as obtained from the measurement at 6 weeks as well as those at 6 months post-surgery and every subsequent 6-month time period through 5 years post surgery:
 - a. Participant impression of overall prolapse improvement at 6-month post-operative intervals as measured by Patients Global Impression of Improvement (PGI-I),
 - b. Mean overall prolapse symptoms at 6-month post-operative intervals based on POPDI-6 scores.
 - c. Duration of postoperative catheterization.
 - d. Urinary function measured at 6-month post-operative time points using:
 - i. Mean UDI-6 scores
 - ii. Hunskaar Incontinence Severity Index
 - iii. Risk of de novo voiding dysfunction
 - iv. Risk of de novo incontinence

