Duration of post-operative catheterization	Continuous	Time to removal of the catheter post-operatively obtained directly from CRF data.
Urinary functional distress as measured PFDI-SF Urinary Distress Inventory scale at 6- month post-operative intervals	Continuous	The PFDI-SF UDI scale will be computed at 6 month post-operative intervals using standard scoring algorithms described by Barber (2006) to create a measure scaled 0 to 100 at each time point. If data at any month are missing, the outcome variable will be coded as missing for that month. All longitudinal analyses or time-specific analyses will use all available data.
Incontinence severity at 6- month post-operative intervals as measures by the Hunskaar Incontinence Severity Index	Ordinal	The ISI scale will be computed at 6-month post operative intervals using the standardized scoring algorithm to generate an ordinal scale (no incontinence or incontinence levels of slight, moderate, severe, or very severe) as described by Sandvik (2000).
Risk of de novo voiding dysfunction defined at 6- month post-operative intervals (evaluated in aggregate fashion)	Binary	Defined as any incidence of a specific voiding dysfunction based on patient-supplied AE information. Rather than reporting data at six-month intervals, results will be aggregated across the follow-up period based on decision at masked review.

Variable	Туре	Definition
Risk of de novo incontinence defined at 6-month post- operative intervals (evaluated in aggregate fashion)	Binary	Defined as any incident case of new or worsening stress urinary incontinence or new or worsening urgency urinary incontinence as reported on either the Patient-reported AE forms or on the complication form obtained at six-month intervals. Based on masked data review, results will be aggregated across the reporting period rather than evaluated at six-month intervals

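### Day-1 catheter removal is prescribed for the Uphold arm only, while time to catheter removal is compared between arms as a secondary efficacy outcome

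*Protocol*

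**What the plan says.** Protocol J.2 has three lists. The Uphold list closes with item 9: "Placement of a vaginal pack and Foley catheter removed on POD1". The uterosacral ligament suspension list has seven items; none mentions a catheter or a pack, and item 6 reads "Other aspects of the suspension procedure will be left to surgeon preference but will be recorded". The list headed For all procedures standardises several points of shared care, for example "Prophylaxis against deep vein thrombosis is required for all participants", but is also silent on catheter and pack.

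Catheter time is an outcome in both documents. Protocol M.2 (Secondary Aim 1) has "urinary function including duration of post-op catheterization". SAP 3.2 places it under "Functional measures of treatment efficacy in the two treatment arms". SAP 9.2 makes it a continuous variable: "Time to removal of the catheter post-operatively obtained directly from CRF data". SAP 7.5 describes the same item as a categorical measure with five classes, from no catheter to more than 4 weeks; every removal within the first week after some catheter use falls in a single class.

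**The concern.** An outcome can show the effect of an operation only if the care that determines it is delivered by the same rule in both arms, or is left equally free in both. Here the day of removal is itself the measured quantity. Read as written, the protocol sets it in the mesh arm, while in the hysterectomy arm it is left open and falls to a surgeon who, under J.3, cannot be masked. If hysterectomy-arm catheters are habitually removed later, Uphold looks better; if earlier, Uphold looks worse. Either can happen with no difference in bladder function.

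The Secondary Aim 1 results go into the primary paper (Protocol M.2), and the SAP's analyses also feed the manufacturer's FDA report (SAP section 2). SAP 7.7 calls the secondary analyses exploratory. That limits what may be claimed from a p-value, but it does not remove bias from the estimate.

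**Working it through.** **1. The lists side by side.**

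| Item | Uphold list | Suspension list | For all procedures |
|---|---|---|---|
| Catheter removal | Day 1 (item 9) | Silent | Silent |
| Vaginal pack | Required (item 9) | Silent | Silent |
| Thrombosis and antibiotic prophylaxis, cystoscopy | – | – | Both arms |

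The protocol has a place for shared perioperative care, and the catheter and pack rules are not in it. No analysis section adjusts for catheter practice or tells the reader to allow for it.

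**2. What the comparison estimates.** Write the difference in mean catheter time as D = (effect of the operation) + (effect of the removal rule). If a fraction f of hysterectomy-arm women keep the catheter d days longer purely by habit, the second term is f × d. For example, 0.5 × 1 day = 0.5 day, and 0.25 × 2 days = 0.5 day. The documents give neither f nor d, nor their sign.

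**3. How visible such a term would be.** The plan states no SD, effect or power for catheter time, so there is no figure to reproduce. What follows is an illustration only. The SAP display shells show 88 and 87 women, so take n = 87 per arm and a two-sided 0.05 level. The SDs and shifts are assumptions.

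Power ≈ Φ( shift / (SD × √(2/n)) − 1.96 ), with √(2/87) = 0.152.

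For a 0.5-day shift and SD 1: 0.5/0.152 = 3.30; 3.30 − 1.96 = 1.34; Φ(1.34) = 0.91.

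| Rule-driven shift | SD 1 day | SD 2 | SD 3 | SD 5 |
|---|---|---|---|---|
| 0.25 day | 0.38 | 0.13 | 0.08 | 0.05 |
| 0.5 day | 0.91 | 0.38 | 0.19 | 0.10 |
| 1 day | >0.99 | 0.91 | 0.59 | 0.26 |

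A false signal is likely when durations are tightly grouped and unlikely when they are widely spread. The shift in the estimate is there in every cell.

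**4. Dependence on which definition is used.** Removal on day 1 and removal on day 2 fall in the same class in SAP 7.5, so the categorical version would show nothing. The continuous version in SAP 9.2 would show the whole shift. The two definitions can give different answers to the same question.

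**The case against.** The case on the other side is substantial.

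- **Silence is not a difference in care.** Surgeons may have treated both arms alike. Protocol J.1 says that they received videos "along with a detailed written description of the technique and guidelines for concurrent procedures", which are not reproduced. This stands: the actual difference between arms is unknown. It is a reason to tabulate practice, since the documents do not show that practice was equal.
- **A removal day does not fix duration.** A woman who cannot void is catheterised again, and classes running beyond 4 weeks show that the authors expected spread. This stands and limits the claim to part of the outcome.
- **Voiding problems are captured elsewhere.** The 6-week residual, urinary retention and voiding at discharge are planned, so a problem after Uphold need not stay hidden. This stands, and these measures supply the remedy.

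A reader might also infer more than the documents support:

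- **Blood loss is confounded in the same way.** The Uphold list opens with "Hydrodissection of the vaginal walls will be performed with at least 30 cc of 0.25% bupivacaine with epinephrine or dilute Pitressin", which the suspension list lacks. But this is step 1 of the assigned technique, hence part of the strategy being compared, and the pack follows vaginal closure, so it cannot explain most intraoperative loss.
- **Early pain is biased by the infiltration.** Protocol Table 4 has no perioperative Surgical Pain Scale entry; the scale resumes at 6 weeks, and SAP 10.2 directs the pain data at the period after that.
- **The pack unmasks participants.** Nothing says that hysterectomy patients receive none, or that a participant would know what a pack signifies. Unblinding and its cause are asked about every 6 months.

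**Conclusion.** The asymmetry is in the current text, and it touches a quantity that the SAP analyses as efficacy. A between-arm difference in raw catheter time may therefore partly reflect a one-sided rule. Its size and direction cannot be derived from the documents; the table above rests on assumed shifts and SDs.

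It would be tempting to conclude that a spurious significant result is nearly certain. That follows only if every Uphold catheter comes out on day 1 and none is replaced, which leaves almost no variance in that arm, and the SAP's own duration classes argue against it.

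The point is confined to an exploratory secondary outcome. The primary outcome and the sample size do not depend on it. It merits correction because the correction is cheap and because the result will be reported alongside the primary one.

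**What to change.** **Protocol J.2.** The investigators should reconcile the lists so that catheter and pack care either fall under one common instruction for both arms, or are left to the surgeon and recorded in both. Which instruction applies is for them. Section T dates the last operation to January 2015, so for this cohort the reconciliation can only state what applied.

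**SAP.**

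- Report raw catheter time descriptively, with actual catheter and pack practice by arm where recorded. Infiltration use may be tabulated next to blood loss, as context only.
- Base the early-voiding comparison on measures that depend less on the removal day: a 6-week residual above 150 ml that is new since surgery (Protocol section I), and urinary retention (SAP Tables 4 and 5). Use spontaneous voiding at discharge as support only, since a catheter left in by choice also affects it. SAP 9.2 currently defines new voiding dysfunction from patient-supplied adverse-event information, so the residual-volume definition has to be added there.
- Settle on one definition of catheter duration across SAP 7.5 and 9.2.

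**Cost.** A wording change in J.2, one or two variable definitions and a footnote; prospectively, also a few tick-boxes on the operative form. The downside is slightly less freedom for surgeons if a common instruction is chosen, and a less simple catheter outcome.
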